The treatment sample will be 144 subjects with PTSD as a consequence of any trauma (e.g., motor vehicle and accidents, burns and other injuries, combat, World Trade Center attack, etc.) ($n=114$), as well as telemedicine subjects with PTSD who live in Vermont, New York State, New Jersey, Connecticut, and Pennsylvania ($n=30$). Subjects will be randomly assigned to one of two treatment groups: imaginal exposure (IE) plus DCS ($n=72$) or IE plus placebo ($n=72$). Both experimental treatment groups will complete a standardized exposure therapy protocol similar to the IRB-approved protocol of the PI's current DCS VR exposure therapy study. The therapy is 12-14 weekly sessions that include well-validated and widely used cognitive-behavioral treatment (CBT) interventions: imaginal exposure, graduated in vivo exposure, psycho-education, relaxation training, engaging in pleasurable events, and cognitive reframing. Subjects will be instructed to take the pill they are provided (i.e., DCS or placebo) 90

minutes prior to all sessions that include exposure (sessions 3 on) and compliance will be assessed weekly. To assess emotional engagement and habituation during imaginal exposure, in 5-minute intervals, the subject rates his/her Subjective Units of Distress (SUDS) level, with 0 indicating no distress and 100 indicating the maximum. (Treatment is described under Section A.7 and a treatment manual is attached in Appendix A.) During treatment, subjects will be assessed by an independent evaluator after sessions 3, 6, and 10, to determine at what point, if any, differences between groups begin to emerge. Subjects will complete a limited battery of self-report questionnaires on a weekly basis prior to the treatment session and will be assessed for potential side effects at each session in which medication is taken.

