Study-specific instruments include (1) the Patient Information Profile, a questionnaire assessing demographic information; (2) Expectancy of Therapeutic Outcome, a 3-item scale that evaluates the credibility of the treatment program used in the PI's other exposure therapy protocols; the (3) Usefulness of Treatment Inventory²⁷ which assesses preferences and usefulness of the specific skills and interventions, and is also used in the PI's other treatment studies; the Working Alliance Inventory Short Form⁵², which measures therapeutic alliance; the Client Satisfaction Questionnaire⁵³, a treatment satisfaction measure; (4) Medication Side-effect Checklist, created by our research group to assess the 18 symptoms that have been named as potential side effects of DCS. The participant is asked to rate how much they experienced each symptom on the day the medication was taken on a 5-point Likert scale ranging from —not at all to —extremely. Any medical problems and medication taken since the last session (including dosage and frequency) will also be recorded. Study-specific instruments are attached in Appendix B. Telemedicine patients will complete these measures online as well as an online version of Telemedicine Satisfaction and Acceptance Scale⁵⁴, which assesses satisfaction with the videoconferencing technology used, and submit electronically using a secure site Internet site so that the clinician at WCMC will have access to this data before each session begins. Homework will be completed on hard copy and then scanned in to a computer and transmitted electronically (by fax or e-mail) to the clinician at WCMC. In addition to these instruments, all subjects will be genotyped for the BDNF SNP (Val66Met) by standard PCR methods from saliva samples. At the beginning of the first meeting, subjects will be asked to rinse their mouths with water and then salivate into a cup. Samples will be collected using the universal identifier for that subject, and transferred to the laboratory of [name] located in the Lasdon building, in batches for processing. (Telemedicine patients will receive assistance from local site staff and/or study assessor with the collection of saliva samples and mailing to [name] laboratory at WCMC). Collection of saliva samples is non-invasive, reducing risks to both subjects and staff. Saliva samples will be collected using the Oragene system (DNA Genotek), which provides a number of benefits for a study with the proposed design. Primarily, samples can be stored at room temperature for extended periods of time.

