Medication Administration: Subjects in the present study will take a standard dose of 100mg of DCS or a placebo capsule orally one time per week 90 minutes prior to each IE therapy session. The dosing regimen is based on the Ressler et al² study and our current protocol, #0411007625, which show that there was no difference in efficacy between the 50 and 500 mg dose, and on the Hoffman study³ showing that 50mg was an effective dosing for social anxiety disorder. Thus, we are proposing to use a dose that will minimize the likelihood of side effects, and which is also consistent with our ongoing pilot study which includes a 100 mg dose. There were no reports of significant side effects in the Ressler study², the

Hoffman study³, or the studies of human memory¹⁴⁻¹⁵ at doses of up to 500mg, and we have not observed any in our pilot study thus far. Thus, DCS appears to be well tolerated when delivered as proposed for this project. The study physicians, [name]., and [name]., will be available to evaluate subjects who experience any side effects in response to the medication.

We will use weekly dosing, occurring 90 minutes before the exposure sessions, because this dosing regimen was effective in the animal and human fear extinction studies^{2, 37-38} and because there is evidence that daily, longer-term dosing can reduce the cognitive enhancing effects of DCS³⁹, possibly due to desensitization of the NMDA receptor over time with daily dosing⁴⁰. The chosen dosing regimen will allow sufficient time for the medication to be absorbed into the bloodstream, and will allow the exposure session to be completed while circulating levels of the medication are still robust. Subjects will be instructed to take the dose of DCS 90 minutes prior to the start of the exposure session, because previous work in humans has shown that peak cerebral spinal fluid concentrations occur at 2 hours following a single oral dose of 250mg DCS⁴¹ and that peak blood levels occur within 3-4 hours after dosing. DCS has a half-life of 10 hours⁴²⁻⁴³. In the Ressler et al. study², DCS was given 2-4 hours prior to exposure sessions, and in the Hofmann et al study³ 1 hour prior to each exposure session. Similarly, the weekly dosing strategy used in the 2-week acrophobia and 5-week social anxiety treatment trials, and our own 10-week study, support the use of a weekly dosing strategy.

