Following the procedures employed in our current DCS study, matching drug and placebo capsules will be prepared by the Research Pharmacy at the University of California, San Francisco. The pharmacy will pulverize 250mg capsules of DCS and 100mg of powder will be packed into a capsule. Lactose powder will be used for the placebo capsules. Randomization and drug dispensing will be performed by the Research Pharmacy of New York Presbyterian Hospital. Medication will be mailed to participants receiving treatment via telemedicine in New York State, New Jersey, Connecticut, Pennsylvania, and Vermont.

Therapy Protocol: The manual is attached in Appendix B. The protocol is 12-14 weekly 75-min. sessions. The number, frequency and length of IE sessions was chosen to be consistent with our DCS study and the DCS phobia treatment study by Ressler and colleagues² and closely follows the procedures adapted from the PI's DCS and other PTSD treatment projects⁴⁴⁻⁴⁵. During ET, the subject recounts a detailed description of the traumatic event until anxiety is sufficiently reduced (ideally, 50%), while the therapist monitor the subject's self-reported distress every five minutes. As described, treatment also includes empirically-supported, widely used CBT components⁵: (1) psycho-education for the subjects and significant other; (2) relaxation training; (3) in vivo exposure, in which the subject creates a hierarchy for avoided situations and confronts these outside of session; (4) behavioral activation (participation in pleasurable events); and (5) cognitive techniques (e.g., reframing, adaptive self talk, etc.).

Session	Components of Treatment
1	Psycho-education : subject learns about common reactions to trauma and PTSD. Review treatment plan : introduce and provide the rationale for all interventions
2	Anxiety Management Techniques : controlled-breathing, guided-imagery relaxation, exercise, and engaging in pleasurable events Psycho-education for family member/significant other : subject brings family member/SO to session and person learns about common reactions to trauma and PTSD.
3	Anxiety Management Techniques : review between session work Imaginal Exposure : target 45 minutes Introduction to Cognitive Therapy Techniques : adaptive self talk

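### The graded 18-symptom side-effect checklist covers only the day of the capsule; overnight and next-day symptoms rest on an unprompted, ungraded record, although much of the dose may still be present

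*Combined protocol and SAP*

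**What the plan says.** The Research Design and Methods section lists, among the study-specific instruments, a Medication Side-effect Checklist that the group wrote itself "to assess the 18 symptoms that have been named as potential side effects of DCS". On a 5-point scale the participant is asked to "rate how much they experienced each symptom on the day the medication was taken". The protocol describes no rating of these items for the following night, the next day or the rest of the week.

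A second, broader record follows directly: "Any medical problems and medication taken since the last session (including dosage and frequency) will also be recorded". It spans the whole interval between sessions, but as described it is open. It does not take the participant through the 18 symptoms and has no severity scale.

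On timing, the same section says subjects are "assessed for potential side effects at each session in which medication is taken". Section A7 (Medication Administration) has the capsule taken "orally one time per week 90 minutes prior to each IE therapy session", and states that "peak blood levels occur within 3-4 hours after dosing" and that "DCS has a half-life of 10 hours". On session length and spacing, the Therapy Protocol says: "The protocol is 12-14 weekly 75-min. sessions".

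The documents do not give the clock time of sessions or capsules, do not say when the rated day ends, and do not say whether the checklist is completed at the dosing session or at the next one.

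**The concern.** The rating window does not match the kinetics that the protocol itself cites. With a blood peak at 3 to 4 hours and a half-life of 10 hours, drug is still present well after the dosing day for any ordinary daytime appointment. A symptom that starts overnight, or starts on the day and continues or worsens the next morning, is not asked about by name and is not graded.

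A window tied to the day, and not to the capsule, also varies in length. A morning participant is rated over many hours after the peak and an evening participant over few. Ratings are then not strictly comparable between participants, or between sessions held at different times.

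At stake is the strength of the tolerability evidence. Section A7 rests its choice of regimen partly on keeping side effects unlikely, and this checklist is the only structured instrument described that can test that. If effects of DCS do begin or persist after the dosing day, the prompted ratings would miss them on DCS with no matching drug effect to miss on placebo, and the difference between arms would look smaller than it is.

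**Working it through.** The protocol states no figure for residual drug, so there is nothing of its own to reproduce.

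**Inputs from the documents**
- Half-life 10 h; blood peak 3 to 4 h after dosing (A7, Medication Administration).
- Capsule 90 minutes (1.5 h) before the session (A7); session of 75 minutes (1.25 h) (Therapy Protocol).
- Rating window: the day of the capsule (Research Design and Methods).

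**Assumptions, not in the documents**
- Capsules between 07:30 and 18:30, so sessions start between 09:00 and 20:00.
- The rated day ends at midnight.
- First-order elimination.

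**Step 1. Simple decay.** Fraction left = 0.5^(t/10), with t the hours since the capsule.

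| Capsule | Hours to midnight | Fraction left at midnight |
|---|---|---|
| 07:30 | 16.5 | 0.5^1.65 = 0.32 |
| 10:00 | 14 | 0.5^1.4 = 0.38 |
| 14:00 | 10 | 0.5^1.0 = 0.50 |
| 17:30 | 6.5 | 0.5^0.65 = 0.64 |
| 18:30 | 5.5 | 0.5^0.55 = 0.68 |

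Independently of clock time: 24 h after the capsule 0.5^2.4 = 0.19; 48 h 0.5^4.8 = 0.036; one week (168 h) 0.5^16.8, or about 0.00001.

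**Step 2. Allowing for absorption.** One-compartment oral model with complete absorption: ke = ln 2/10 = 0.0693 per hour, and ka chosen so that ln(ka/ke)/(ka − ke) equals the time of the peak. Peaks at 3, 3.5 and 4 h give ka = 0.938, 0.750 and 0.615. Amount in the body = ka/(ka − ke) × (e^(−ke·t) − e^(−ka·t)).
- 07:30 capsule (t = 16.5 h): 0.34, 0.35, 0.36.
- 18:30 capsule (t = 5.5 h): 0.73 for all three.

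The range moves from 32–68% to about 34–73%, so the conclusion does not depend on the simple model.

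**Step 3. Length of the window.** It runs from 16.5 h (07:30) to 5.5 h (18:30). The blood peak falls at 10:30–11:30 for the first and 21:30–22:30 for the second, leaving 12.5 to 13.5 h and 1.5 to 2.5 h of rated time after the peak. In both cases the peak lies inside the rated day.

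**Step 4. When the form is completed.** If at the dosing session, it can cover only the first 1.5 to 1.5 + 1.25 = 2.75 h after the capsule, which ends before the stated 3 to 4 h peak; the midnight figures then do not apply, because the window closes sooner. If at the next session, steps 1 to 3 apply. Either way the 18 symptoms are not rated for the next day.

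**The case against.** The strongest reply has five parts.

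- **Later effects are recorded.** The open item covers the whole week, and study physicians are available to evaluate side effects. This stands. A reader might infer that nothing is captured after the dosing day, and the documents do not support that. The gap is confined to prompted, graded symptoms.
- **Midnight and the clock times are not the protocol's.** This also stands: the range in the working is conditional on assumptions, and the protocol's half-life alone does not yield it. The checklist itself sits in an appendix outside the public text, so its instructions may define the day. But a day ending at bedtime shortens the window, and one that includes the night still leaves the next day unrated.
- **Residual drug is not a missed side effect.** A reader might infer that side effects on DCS are under-counted and the comparison biased toward no difference. The documents do not show this. They give no link between drug level and symptoms and no data on late onset. A7 reports no significant side effects in the cited studies at up to 500 mg, and none so far in the pilot. Under the assumed times the period of highest exposure lies within the rated day.
- **Both arms use the same window.** Comparison of same-day symptoms stays fair, and randomisation should balance appointment times on average. The Statistical considerations section specifies no between-arm side-effect analysis that would be distorted. What remains is possible loss of later or persisting symptoms.
- **Changing the form has a price.** The protocol says its instruments match those of the group's ongoing DCS study. Replacing the same-day item would lose that comparability, and a wider window brings in background symptoms. This argues for adding a rating, not replacing one.

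**Conclusion.** The point holds as a minor one. The only graded side-effect rating described is limited to the day of the capsule, and later effects rely on a record that neither prompts nor grades the 18 symptoms. With the stated half-life, roughly 30% to 70% of the dose may remain at midnight and 19% at 24 hours. The first figure assumes first-order loss, capsules between 07:30 and 18:30 and a day ending at midnight; the second needs only first-order loss at the stated half-life. On those assumptions the rated window varies about threefold (16.5/5.5 = 3) with appointment time.

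Symptoms that begin or persist overnight or the next day may therefore be missed on DCS. This is a possibility that the design leaves open, not a demonstrated under-count, and it does not touch the CAPS outcome or the sample size.

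**What to change.** Make three small changes to the checklist, leaving the open medical-problem item as it is:

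1. Keep the same-day rating, so that it stays comparable with the pilot, and state when that day ends.
2. Add a second column rating the same 18 items on the same scale, from the end of that day to a fixed time after the capsule, for example 24 to 48 hours. By the stated half-life, 19% of the dose remains at 24 hours and 4% at 48 hours, so the later limit covers nearly all of the exposure. Complete it at the next contact, whether or not a capsule is taken then, and say so in the protocol.
3. Record the clock time of each capsule, so that the length of the same-day window is known.

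The cost is a form change needing notice to the IRB, slightly longer recall (usually about a week after the capsule), and some background symptoms, which are expected in both arms. Keeping the two columns separate stops those background symptoms from diluting the same-day rating. Dosing and clinical management are unaffected.

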Weill Cornell Medical College

┌ NewYork-Presbyterian Hospital
└ Weill Cornell Medical Center

IRB Protocol Number: 0802009646
Clinicaltrials.gov ID: NCT00875342

Title: D-cycloserine Enhanced Imaginal Exposure Therapy for Posttraumatic Stress Disorder (PTSD)

Coordinating Center: Weill Cornell Medical College, Department of Psychiatry

IRB Protocol Version and Date:

Version dated December 11, 2009

No substantial amendments since December 11, 2009

SUMMARY

Posttraumatic stress disorder (PTSD) is a serious mental health condition that can develop after exposure to a traumatic event, such as an accident. Research has found that cognitive-behavioral treatment with exposure therapy, and also antidepressant medications, are effective treatments for PTSD. Cognitive-behavioral therapy involves learning more adaptive ways to interpret trauma-related memories and engaging in activities that help recovery from trauma, i.e. relaxation. Imaginal exposure therapy involves subjects repeatedly recounting memories of their trauma, within a controlled, supportive environment. However, research also shows that these treatments are not effective in as many as half of all subjects. The goal of this study is to develop more effective PTSD treatments. The study tests whether adding an antibiotic drug, D-Cycloserine (DCS), to cognitive-behavioral treatment with exposure therapy will make the treatment more effective. Pilot research studies suggest that DCS enhances the therapeutic effects of exposure therapy for subjects who have a fear of heights and for those with social anxiety. This study compares cognitive-behavioral treatment with exposure therapy plus DCS, versus cognitive-behavioral treatment with exposure therapy plus a placebo (sugar pill), to test whether subjects given the DCS will show a faster and larger improvement in their PTSD symptoms. Patients living in areas that are not geographically proximal to the Weill-Cornell Medical Center New York City campus will receive cognitive behavioral therapy using telemedicine (videoconferencing technology) as a way to investigate the feasibility and acceptability of using this technology to increase access to care for patients with PTSD.

RESEARCH DESIGN AND METHODS

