For patients outside of the Burlington area, we will use other Internet-based videoconferencing (e.g. Skype, Adobe Connect) to connect participants with the therapist, when Polycom equipment is not available. Multiple HIPAA-compliant Internet-based videoconferencing systems (e.g., Polycom, Skype, or Adobe Connect) will be used to connect the patient with the therapist, depending on what technology is available and is most appropriate to each subject's situation. In this way, we hope to increase flexibility and accessibility and decrease cost.

After providing written informed consent, consecutively referred survivors of a variety of traumas will be assessed to determine initial eligibility for the study. See Section A6 for inclusion/exclusion criteria. An independent evaluator (unaware of treatment condition) will assess symptoms of PTSD and other psychopathology using structured clinical interviews and self-report measures with well-established psychometric properties at pre-treatment, during treatment, immediately post-treatment, and at six-month follow-up. Subjects who are diagnosed with a psychiatric disorder but who do not meet the inclusion criteria will be offered a referral for treatment to an appropriate provider. Prior to treatment subjects will also meet in person (or by video for telemedicine participants) with one of the two study physicians, [name]. and [name]., for medical clearance to participate. The physician will review each subject's medical history to ensure they have no contraindications to DCS treatment.

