4	Anxiety Management Techniques : review between session work Imaginal Exposure : target 45 minutes Reinforce Adaptive self talk Introduction to In Vivo Exposure : creation of hierarchy
5	Anxiety Management Techniques : review between session work Imaginal Exposure : target 45 minutes In Vivo Exposure : subject reviews assignment and plans next assignment Cognitive Therapy : Teach restructuring, types of maladaptive thoughts, thought monitor
6-11	Anxiety Management Techniques : review between session work Imaginal Exposure : target 45 minutes In Vivo Exposure : subject reviews assignment and plans next assignment Cognitive Therapy : reinforce restructuring, review thought monitor
12	Wrap up : Review of skills learned and progress in treatment Note: if clinically indicated, treatment can be extended to include up two 2 additional exposure therapy sessions, for a total of 14 sessions.

Statistical considerations (e.g. justification for sample size or “n”):

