 Sample size estimates were based on the formula outlined by Diggle et al.⁴⁶ for longitudinal studies. Although our pilot data and the published DCS phobia treatment studies suggest large effect sizes for a combined DCS treatment, we followed the recommendations by Kraemer et al.⁴⁷ who suggested that the critical effect size at which the power is computed to be 80% should be the threshold below which clinicians are unlikely to be interested in the effect. Adopting the procedures used in a large-scale study of Vietnam Veterans with PTSD⁴⁸, we designated a decline of 10 points on the CAPS (based on ½ a standard deviation) as the minimum clinically meaningful effect, which corresponds to a conservative (small-moderate) estimated effect size of $d = .5$. The calculations were based on the assumption of a strong correlation within subjects over time, $\rho = .6$, and also assume $\alpha = .05$. The number of assessments for the primary outcome measure (CAPS scores) was 5 (baseline, 3 clinical assessments during treatment, and post). A sample size of 34 per group was found to be sufficient at 80% power to detect the effect. Estimating an attrition rate of 30%, we plan to enroll 114 (57 per group) to ensure that an adequate sample remains by post-treatment and follow up. In addition, pilot subject data ($n=10$) will be collected to investigate the feasibility and acceptability of telemedicine to provide imaginal exposure (IE) therapy for PTSD.

Literature Cited:

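### Does a post-treatment CAPS that moves with a 12-14 session therapy distort the DCS comparison enough to need a fixed assessment point?

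*Combined protocol and SAP*

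**What the plan says.** Under A7 (Therapy Protocol), "The protocol is 12-14 weekly 75-min. sessions". The session table places imaginal exposure in sessions 3 to 11. Session 12 is a wrap-up, described as "Review of skills learned and progress in treatment", with the note that "if clinically indicated, treatment can be extended to include up two 2 additional exposure therapy sessions, for a total of 14 sessions". The visible text gives no criterion for extending; the treatment manual, in an appendix not seen here, may do so.

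Research Design and Methods has an evaluator unaware of treatment condition assess patients "at pre-treatment, during treatment, immediately post-treatment, and at six-month follow-up". The assessments during treatment come "after sessions 3, 6, and 10, to determine at what point, if any, differences between groups begin to emerge". No week or session number is given for the post-treatment visit.

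The Summary states the aim as "to test whether subjects given the DCS will show a faster and larger improvement in their PTSD symptoms". Statistical considerations says "The number of assessments for the primary outcome measure (CAPS scores) was 5 (baseline, 3 clinical assessments during treatment, and post". It names no analysis model and no primary time point.

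**The concern.** Of the treatment-phase CAPS assessments after baseline, three are tied to a session number. The fourth, post, is tied to the end of treatment, which a clinical decision after randomisation can move. An extended patient is scored after up to two more exposure sessions than other patients.

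If that decision follows poor response (a natural reading, though not stated), and DCS speeds response as hypothesised, placebo patients would be extended more often even with blinding intact. Their extra therapy would then be counted at the visit where the larger-improvement claim is most naturally read. At stake would be a smaller difference and lost power at post. The proposed answer is to take post at the regular session-12 point, before any extension session.

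**Working it through.** **Session counts.** Exposure in sessions 3-10 gives 8 sessions before the session-10 CAPS. Sessions 3-11 give 9 before an unextended post. With full extension, 9 + 2 = 11. The count of 9 to 11 and the two-week range are correct.

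**The plan's own figure.** Inputs from Statistical considerations: m = 5 assessments, correlation 0.6, d = 0.5, alpha 0.05, 80% power. The average-difference formula is n = 2(z_alpha + z_power)² [1 + (m-1)rho] / (m d²).

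- One-sided: 2 × (1.645 + 0.842)² × 3.4 / (5 × 0.25) = 33.6, so 34, the stated figure.
- Two-sided: 42.7, so 43.

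The stated 34 therefore matches an average over five assessments, of which only one can move.

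**When the difference narrows.** Let p be the share extended, g the CAPS gain per extra session, and D the difference at a fixed point before extension. If every extended patient takes both extra sessions, then

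moving difference = D - 2(p_placebo × g_placebo - p_DCS × g_DCS).

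A higher extension rate on placebo is not sufficient; the product must be larger on placebo. At 40% versus 20% extended, narrowing disappears if DCS doubles the gain per extra session.

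**Size, with assumed inputs.** Neither p nor g is in the documents.

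1. Equal gains of 1 to 4 points in both arms, and 10 to 40 percentage points more placebo patients extended: the loss is 2 × g × (difference in p), from 0.2 to 3.2 points, with median 1.0 over 16 combinations.
2. Equal gains contradict the trial's hypothesis. If the 10 points sought accrue evenly over 9 exposure sessions, DCS gains 10/9 = 1.11 points more per session. The loss becomes 2 × (g × difference in p - p_DCS × 1.11).
   - With 20% of DCS patients extended, 2 × 0.2 × 1.11 = 0.44 comes off each combination. The median is 0.56, and 3 of 16 combinations reverse sign.
   - With 40% extended, 0.89 comes off. The median is 0.11, and 8 of 16 reverse.
3. Twelve simulated scenarios used assumed exponential or linear improvement from a mean CAPS of 75, with extension when the score after nine exposure sessions was above 40, 50 or 60. The moving difference minus the fixed difference ran from -0.4 to +0.6. It narrowed in 8 scenarios (most: 7.06 to 6.65, with 47% versus 28% extended) and was unchanged or larger in 4 (for example 5.19 to 5.81). The largest narrowing is 0.41/7.06 = 5.8%, or about 0.6 on a 10-point difference. Further simulations with a difference of about 10 points lost 0.05 to 0.5.

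**Power.** SD 20 (10 points is half an SD), correlation 0.6, 57 × 0.7 = 40 completers per group, two-sided 0.05, normal approximation:

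- Post only, baseline-adjusted: SE = 20√(2 × 0.64/40) = 3.58.
- Slope over five equally spaced visits (times 0 to 4), difference rising to 10: slope difference 2.5, SE = √(2 × 400 × 0.4/(40 × 10)) = 0.894. A loss L at post lowers the slope difference by 0.2L.
- Five-visit average: SE = 20√(2 × 3.4/5/40) = 3.69. A loss L enters as L/5.

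| Loss at post | Post only | Slope | Five-visit average |
|---|---|---|---|
| 0 | 79.8% | 79.8% | 77.4% |
| 0.6 | 74.8% | 75.8% | 76.4% |
| 1.0 | 71.1% | 73.0% | 75.7% |
| 3.2 | 47.6% | 54.8% | 71.8% |

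The slope column treats visits as nominal, equally spaced points. With actual assessment dates and roughly linear improvement, a later post score still lies on the patient's own line. A simulation with 40% versus 20% extended at 2.5 points a week returned 10.0 with actual dates and 9.6 with nominal times.

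**The case for a change.** The strongest case for a change is that post is the only treatment-phase CAPS that moves with a decision taken after randomisation, that the visible text neither defines that decision nor says how extended patients are analysed, and that a timing definition costs little. That the bias could go either way helps this case: as planned, a post difference cannot separate the drug effect from differing therapy length. If post alone carried the conclusion, a 1-point loss would take power from 80% to 71%.

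The facts and the arithmetic stand. So does the point that the exposure depends on an analysis model the text does not name. The five-visit average is the planning formula; it is not a stated model.

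The step to a change does not follow, for three reasons. First, the larger losses need equal gains per session in both arms, and the 3.2-point case is about eight times the largest simulated narrowing (3.2/0.41). Second, both the fixed-length and the flexible-length question are legitimate, and the protocol defines the therapy as 12-14 sessions. Third, a fixed anchor has its own costs:

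- For extended patients, post becomes a mid-treatment score.
- They need an additional interview: 16 to 32 in all if 20-40% of about 80 completers are extended (an assumption).
- Counting six months from the anchor shortens their true follow-up by up to two weeks, which moves the uneven timing to another visit.

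In return, the anchor adds one exposure session to what the session-10 CAPS already measures.

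**Conclusion.** No change follows; this is a fair trade-off. The post CAPS does move with treatment length, but comparing the arms when a 12-14 session therapy ends is a valid randomised comparison of DCS with placebo under that therapy. If the drug has no effect and blinding holds, extension is balanced between arms, so the false-positive risk does not rise. If the drug works, the difference at that one visit may narrow slightly or widen. In the simulations the narrowing was at most about 0.6 of 10 points. That costs about 5 percentage points of power in a post-only test, 4 in a slope with nominal times, and 1 in the five-visit average behind the sample size.

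These sizes rest on assumed extension rates and gains per session, on SD 20 and correlation 0.6 from the plan, and on 40 completers per group. They would be larger if extension were much more common on placebo and extra sessions helped both arms equally.

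Analysts can cover the point within the plan as written: report sessions received and extension rates by arm, use actual assessment dates in any slope model, and show the blinded CAPS after session 10 as the supporting comparison at equal exposure (8 sessions for patients on schedule).
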